STUDY PROTOCOL WITH SAP

Development of Structured Exercise Program for T2DM Management

The Ethics Committee of The Faculty of Medicine Universitas Indonesia
Protocol Number 17-05-0554

CENTER FOR SPORTS AND EXERCISE STUDIES, INDONESIA MEDICAL
EDUCATION AND RESEARCH INSTITUTE, FACULTY OF MEDICINE
UNIVERSITAS INDONESIA

July 24, 2017

Study Protocol with SAP

Title: DEVELOPMENT OF STRUCTURED EXERCISE PROGRAM FOR T2DM MANAGEMENT

Background.

Given the many forms of interval training, it is important to investigate the appropriate intensity, duration, frequency, and type of exercise for diabetic patients. One significant issue for exercise-based T2DM management is oxidative stress, as both high plasma glucose and the exercise itself will increase production of reactive oxygen species (ROS). However, exercise can still play a useful role in good T2DM management. At moderate intensity, yielding low levels of ROS, cell signaling and regulation of gene expression influence the expression of important enzymes associated with the antioxidants that defend against ROS. Therefore exercise programs for patients with Type 2 Diabetes Mellitus (T2DM) must be demonstrably safe, effective, and beneficial.

Objectives.

To review the effect of combined high intensity interval training (HIIT) and resistance training to meet three criteria

- 1) Safe: showing lowered oxidative stress (lowered MDA and higher SOD measure)
- 2) Effective: showing better glycaemic control (lowered HbA1c)
- 3) Beneficial: showing better fitness level (increased VO₂max)

Design

Randomized controlled trial (RCT)

Methods.

- 1) Subject recruitment: T2DM patients who were registered at primary clinics near the training facility
- 2) Eligibility criteria
 - Aged 18–64 years
 - Showing controlled plasma glucose levels (average fasting plasma glucose < 250 mg/dL or HbA1c ≤ 10.5%), with regular intake of oral hypoglycemic agents for at least 6 months.
- 3) Exclusion criteria
 - Suffered from diabetic complications such as
 - macroangiopathy (ECG readings showing signs of coronary heart problems, or foot ulcers),
 - severe retinopathy (severe NPDR)
 - severe nephropathy (macroalbuminuria)

- restricted locomotion

4) Before and after measurements

- Physical fitness included VO₂max, grip strength, sit and reach, and back extension, which was measured using the CSEP protocol
- Blood work for HbA1c, malondialdehyde (MDA) level, and superoxide dismutation (SOD) activity.
- Body composition:body mass index (BMI) and body fat percentage (Bioelectrical Impedance Analysis (BIA) - (Tanita MC780MA portable).
- Quality of Life measure using the EuroQol EQ-5D questionnaire

(One-sided blinding meant that those measuring fitness levels were unaware of subjects' group allocation, and all blood samples were numbered by recruitment order to conceal group allocation.)

5) Subjects were randomly allocated to experimental (EXP) and control (KTR) groups, using block of 4 randomization until there were 25 subjects in each group.

6) Health checks before starting exercise session:

- Resting blood pressure should not exceed 180/100 mmHg
- Heart rate should not exceed 100 per minute
- Random blood glucose level outside 100–300 mg/dL.

7) The 12-week combined high intensity interval training (HIIT) and resistance training was conducted at the Center for Sports and Exercise Studies - Indonesian Medical Education and Research Institute, Faculty of Medicine Universitas Indonesia, Jakarta, Indonesia.

- Detail of HIIT load is shown in Table 1.

Table 1. Dose of high-intensity interval training (HIIT)

Week	Intensity		Duration		Comparable intensity (METs)	Training device
	VO ₂ peak	HRmax				
1–2	50%	60–70%	20 minute continuous		Moderate intensity (3.8)	Treadmill/ Ergocycle
3–6	HIE: 80%	90%	1 min	4 cycles = 20 min	Moderate intensity (4–6)	Treadmill/ Ergocycle
	LIE: 50%	70%	4 min		High intensity (6–8)	
7–12	HIE: 85%	92%	1 min	6 cycles = 30 min	Moderate intensity (4–6)	Treadmill/ Ergocycle
	LIE: 60%	75%	4 min		High intensity (6–8)	

Note:

1. Comparable intensity refers to *compendium of physical activities*.
2. Comparison of VO₂peak to HRmax is calculated using Swain formula.

- The resistance training comprised nine exercises for core, upper, and lower extremities to train all body muscles (single leg raise (leg extension), shoulder press, chair squat, back row, chest press, lateral pull down, hamstring curl (leg curl), back up, and crunches). Detailed of training load is shown in Table 2.

Table 2. Dose of resistance training

Week	Set	Repetition	Load (RPE)	Training device
1–2	1	8	No external weight/minimal (3–4)	Resistant band & dumbbell
3–6	1	10	External weight resistance (5–6)	Weight training machine & weight strap
7–8	2	10	External weight resistance (7–8)	Weight training machine & weight strap
9–12	2	10	External weight resistance (8–9)	Weight training machine & weight strap

8) During the training program, subjects were asked not to alter their daily physical activities, food intake, or medication to ensure that training effects were maintained

- All subjects were provided with OMRON HJ325 pedometers to be worn throughout the study period other than when performing the program exercises.
- Each subject was asked to record their physical activity every four weeks, using Bouchard's three-day physical activity record
- Each subject was asked to record their food intake using 3-day food intake record, which were analyzed using Nutri Survey software (SEAMEO-TROPMED RCCN – University of Indonesia).

Statistical Analysis Plan

- Group numerical data were reported as means \pm standard deviation; non-normally distributed data were reported as median and interquartile range (IQR).
- At the outset, randomization of EXP and KTR groups was tested using independent sample t-testing for mean differences or chi-square testing for differences in proportions.
- Between-group effects were analyzed in terms of post-study and pre-post differences (Δ/delta) measurements, using independent samples t-testing for normally distributed data and independent samples Mann-Whitney U testing for non-normally distributed data.
- Statistical analysis was performed using SPSS (Statistical Package for the Social Sciences) version 20 for Windows.

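### Entry asks for 6 months of regular oral hypoglycaemic intake but not an unchanged regimen, which leaves avoidable noise in the pre-post HbA1c difference

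*Combined protocol and SAP*

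**What the plan says.** Methods item 2 (Eligibility criteria) describes entrants as having controlled glucose "with regular intake of oral hypoglycemic agents for at least 6 months". The glycaemic limit in the same bullet is a level: average fasting glucose below 250 mg/dL, or HbA1c of at most 10.5%. It does not ask that HbA1c be steady.

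Methods item 8 covers the training period, when "subjects were asked not to alter their daily physical activities, food intake, or medication". It says nothing about the time before entry. The protocol describes no run-in, no repeat baseline HbA1c and no record of recent regimen changes.

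Lowered HbA1c is the only measure named under criterion 2 of the Objectives (Effective). Methods item 5 allocates subjects "using block of 4 randomization until there were 25 subjects in each group", and item 7 sets a 12-week programme. The Statistical Analysis Plan compares the arms on two quantities, the post-study value and the pre-post difference, by an independent-samples t-test or Mann-Whitney U test. It does not say which of the two decides whether the programme is effective.

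**The concern.** HbA1c lags behind a change of treatment. The documents do not give the lag; two to three months is assumed here. A patient who has taken tablets regularly for 6 months, but whose dose or drug was changed shortly before baseline, meets the entry criterion as written. That patient's baseline HbA1c still partly reflects the old regimen, and part of the 12-week change will come from the new one, whichever arm is assigned. The request in item 8 starts too late to prevent this.

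The sponsor plainly wants medication held constant so that the effect of training can be read, and the entry criterion leaves part of that aim unmet. At stake is the precision of the HbA1c comparison in a trial of 25 per arm for which no power calculation is given, so no margin is shown for absorbing extra noise.

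**Working it through.** The documents give no SD, effect size, alpha or power for HbA1c, so there is no stated figure to reproduce.

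**Inputs**
- From the protocol: n = 25 per arm, two randomised arms, 12 weeks.
- Assumed: share of entrants with a recent regimen change, p = 0.10 to 0.20; residual drift in each of them, d = 0.5 or 1.0 HbA1c points, the same in either arm; SD of the 12-week change otherwise, s = 1.0 point; two-sided 5% test, normal approximation for power.

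**Step 1: expected bias.** The mean drift in each arm is p × d, which runs from 0.10 × 0.5 = 0.05 to 0.20 × 1.0 = 0.20 points. Randomisation makes it equal in expectation in both arms, so its expected contribution to the between-arm difference is 0.

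**Step 2: added variance.** The variance of the change rises by the fraction p(1 − p)d²/s². The equivalent number per arm is 25 divided by (1 + that fraction). Power is shown for assumed true differences of 0.8 and 0.5 points.

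| p | d | Rise in variance | Equivalent n per arm | Power, 0.8 points | Power, 0.5 points |
|---|---|---|---|---|---|
| none | – | 0 | 25 | 80.7% | 42.4% |
| 0.10 | 0.5 | 0.09 × 0.25 = 2.25% | 25/1.0225 = 24.4 | 79.9% | 41.6% |
| 0.20 | 0.5 | 0.16 × 0.25 = 4% | 25/1.04 = 24.0 | 79.2% | 41.0% |
| 0.10 | 1.0 | 0.09 × 1 = 9% | 25/1.09 = 22.9 | 77.3% | 39.5% |
| 0.20 | 1.0 | 0.16 × 1 = 16% | 25/1.16 = 21.6 | 74.7% | 37.5% |

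**Step 3: is chance imbalance a further harm?** Take p = 0.15 and d = 1.0.
- SE of the between-arm difference without drift: √(2/25) = 0.283.
- SD of the difference caused by unequal numbers of recently changed patients: √(2 × 0.15 × 0.85/25) × 1.0 = 0.101.
- SE with drift: √(2 × 1.1275/25) = 0.300.
- Check: 0.283² + 0.101² = 0.0800 + 0.0102 = 0.0902 = 0.300².

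The imbalance is exactly the added variance, and the observed SD of change carries it into the test.

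**Step 4: which comparison is exposed.** The carry-over sits in the baseline value. With the assumed lag and medication unaltered over the 12 weeks, the final HbA1c largely reflects the new regimen. The pre-post difference takes most of the drift; the post-study comparison takes little of it.

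**The case against.** The strongest reply is that randomisation already deals with this. Both arms admit recently changed patients on the same terms, and the SAP plans only between-group tests. The expected bias is zero, one of the two planned comparisons largely escapes, and every figure for the size is an assumption. In the mildest row of the table, power for a 0.8-point difference moves only from 80.7% to 79.9%. All of that stands, and it keeps the point minor. It does not close the gap in the text: nothing in the documents prevents or records a regimen change just before entry.

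Three stronger readings are tempting, and the documents do not support them.

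- A reader might infer that drift would be mistaken for an exercise effect. That would follow if the Effective criterion were judged on the fall in HbA1c within the exercise arm alone. The wording of the objective does not exclude this, but the SAP plans no within-arm test.
- A reader might add chance imbalance as a second harm: at p = 0.15 and d = 1.0, a 2-SD imbalance gives a spurious difference of 2 × 0.101 = 0.20 points. Step 3 shows that this is the same noise counted again. It is less than one SE (0.300) and does not raise the false-positive rate.
- A reader might suppose that recently changed patients are common, especially among entrants with high HbA1c. The documents show only that such patients could enter.

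**Conclusion.** The point holds as a minor one about precision. The entry criterion does not require a stable regimen, and item 8 does not reach back before the programme. The consequence is extra variance in the pre-post HbA1c difference, with no expected between-arm bias and a valid test. For 10–20% of entrants affected and an SD of 1.0 point, variance rises by 2–4% if the drift is 0.5 points and by 9–16% if it is 1.0 point. In the worst of these cases power falls by 6.0 percentage points for a true 0.8-point difference (80.7% to 74.7%). The share, drift, SD and lag are all assumptions. If few patients changed recently or drift was small, the loss is negligible.

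**What to change.** Add to the second eligibility bullet of Methods item 2 that the glucose-lowering regimen, drug and dose, has been unchanged for a stated window before the baseline HbA1c. The investigators should set its length to cover the HbA1c lag; that is a clinical decision. A patient who does not yet meet the condition is deferred until it holds. The cost is one clause, one item to verify at screening and a few deferred patients. The documents do not say how the 6 months of intake is confirmed, so the source for this check should be named too.

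If nobody is to be deferred, record at baseline whether the regimen changed within that window (yes/no). Then analyse HbA1c by ANCOVA, with the post-study value as outcome and arm, baseline HbA1c and this indicator as terms. Baseline HbA1c alone helps only in part, because a recently changed and a stable patient with equal baselines have different expected courses. This option costs more than an extra screening item: the SAP has only t-tests and Mann-Whitney U tests, so a regression model must be added. The indicator would rest on about 5 to 10 of 50 patients (0.10 × 50 to 0.20 × 50), and if drift is small it may gain little.

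If recruitment is already complete, only this second option remains. It should use information dating from before randomisation, collected without knowledge of allocation.

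### Allocation uses one fixed block of 4 with no described step to hide the next assignment; under stated conditions about 16 of 50 assignments could be foreseen

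*Combined protocol and SAP*

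**What the plan says.** Methods item 5 is the whole description of allocation: EXP or KTR, "using block of 4 randomization until there were 25 subjects in each group". One block size is given. Nothing is said about who generated the list, who held it, who enrolled subjects, or how each assignment was released.

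The only wording on masking is the note at the end of Methods item 4. It has two parts: "One-sided blinding meant that those measuring fitness levels were unaware of" the groups, and "all blood samples were numbered by recruitment order to conceal group allocation".

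Methods item 1 takes subjects from "T2DM patients who were registered at primary clinics near the training facility". Under item 7, the combined interval and "resistance training was conducted at the Center for Sports and Exercise Studies".

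The Statistical Analysis Plan states: "Between-group effects were analyzed in terms of post-study and pre-post differences", by t-test or Mann-Whitney test without adjustment. It also says that "randomization of EXP and KTR groups was tested using independent sample t-testing for mean differences", with chi-square tests for proportions.

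**The concern.** Masking the assessors and coding the blood samples protect measurement after a subject has been allocated. Neither stops the person enrolling from knowing which arm comes next. With a single block size of 4, the fourth assignment in every block is determined by the first three, and the third is determined whenever the first two match. Subjects and trainers necessarily know who trains, so past allocations may become known to others.

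A recruiter who can foresee the next arm may, without intending to, time the entry of fitter or more motivated patients. The groups then differ at entry for a reason other than chance. An entry difference that lasts to week 12 biases the unadjusted comparison of post-study values. The same stable difference cancels in the pre-post delta. A difference that fades by week 12 does not cancel there, and neither does selection on 12-week change unrelated to training.

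**Working it through.** **Inputs from the plan.** Block size 4, two arms and 25 per arm (Methods item 5). I infer 1:1 allocation, so each block holds two EXP and two KTR. No stratification is mentioned, so I take one list. The plan gives no predictability figure to reproduce.

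**Conditions assumed.** Subjects are allocated one at a time, the recruiter knows the block size, and the recruiter sees past allocations.

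**Certain assignments.** There are 6 equally likely orders of a block. EEKK and KKEE leave 2 certain places each; EKEK, EKKE, KEEK and KEKE leave 1 each.
- Mean per block = (2×2 + 4×1)/6 = 8/6 = 4/3.
- 50/4 = 12.5, so there are 12 complete blocks and a last pair. Certain places = 12 × 4/3 = 16 of 50 (32%).
- The count is 12 + Binomial(12, 1/3): range 12 to 24, SD 1.6, and more than 16 in 37% of lists.
- A recruiter who also uses the 25:25 total knows the 50th assignment: 16 + 1 = 17 (34%).

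**Best-guess accuracy.** Expected correct guesses by place in the block are 1/2, 2/3, 2/3 and 1, which sum to 17/6. The last pair is forced to one per arm and adds 1.5. Total = 12 × 17/6 + 1.5 = 35.5 of 50, or 71.0%. If past allocations are not seen, accuracy is 50% at any block size.

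**Illustrative effect on the post-study comparison.** Assumptions: no true treatment effect; a shift of 0.10, 0.25 or 0.50 SD at entry that lasts to week 12; steering on certain assignments only; two-sided t-test at 5% (the plan states no level). On average 8 of the 16 certain places are EXP and 8 are KTR.
- *Favourable patients into EXP only:* mean false difference = 8/25 × shift = 0.32 × shift.
- *Less favourable patients also into KTR, by the same amount:* 8/25 + 8/25 = 0.64 × shift. The gap between steered patients is then twice the shift: 0.20, 0.50 or 1.00 SD.

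| Shift (SD) | EXP only: false difference (SD) | EXP only: type I error | Both directions: false difference (SD) | Both directions: type I error |
|---|---|---|---|---|
| 0.10 | 0.03 | 5.2% | 0.06 | 5.5% |
| 0.25 | 0.08 | 6.0% | 0.16 | 8.4% |
| 0.50 | 0.16 | 8.5% | 0.32 | 18.5% |

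Type I errors are from simulated trials of 25 per arm, with no-shift controls near 5%.

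**Delta comparison.** A stable shift is the same before and after, so it drops out: about 5% at every shift size.

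**Baseline test.** A lasting shift has the same size at entry as at week 12. A 5% t-test at baseline therefore flags it about as often as the post-study test rejects: roughly 6% or 8% of the time for 0.25 SD. A non-significant baseline test offers little reassurance.

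**Varying blocks.** For blocks of 4 and 6 with equal odds, constrained to 50 subjects, and an observer who knows both sizes, 6,000 simulated lists per setting gave:
- total not used: 2.9 of 50 certain (5.7%), against 16 with fixed blocks;
- total used: 4.3 of 50 certain (8.6%), against 17;
- best-guess accuracy near 69% in both, against 71.0%;
- running imbalance of at most 3, against 2.

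**The case against.** The strongest reply is that silence is not absence. The document is a short summary in the past tense, and concealment may have been used without being described. That stands.

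All three enabling conditions are also undocumented. Filling the arms "until there were 25 subjects in each group" and numbering samples by recruitment order fit one-at-a-time allocation but do not prove it. If a group already enrolled was allocated together, nothing could be foreseen. Patients were registered at primary clinics while training took place at the Center, which gives some reason to doubt that a recruiter saw past allocations. This also stands, and it makes every figure conditional.

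The size of the harm is open to challenge too. A reader might take 18.5% as the expected type I error. It requires a 0.50 SD shift and steering in both directions, so a gap of 1.00 SD between steered patients. Nothing in the plan suggests that less favourable patients would be directed to KTR, and with steering into EXP only the figure is 8.5%.

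A reader might also infer that choosing patients likely to respond to training would inflate the delta comparison. The documents do not support this: the plan describes no training for KTR, and a type I error calculation supposes that training has no effect, which leaves no training response to select on.

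Finally, a block of 4 is a conventional choice, and varying the blocks barely lowers best-guess accuracy. That is true, but it does remove most of the certain predictions at almost no cost.

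**Conclusion.** The concern holds in a limited form. The plan names one fixed block of 4 in a trial that cannot mask subjects or trainers, and it describes no protection of the next assignment. If allocation is one at a time, the block size is known and past allocations are seen, 16 of 50 assignments on average (32%, range 12 to 24) are certain and 71% can be guessed correctly. If past allocations are hidden, or the whole group is allocated together, the problem disappears.

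The likely distortion is small to moderate and falls mainly on the post-study comparison: type I error of 5.2% to 8.5% with steering into EXP only, and 5.5% to 18.5% with equal steering in both directions, over assumed shifts of 0.10 to 0.50 SD. The delta comparison is protected against a stable shift, but not against one that fades or against selection on change unrelated to training. A reader might conclude that allocation was unconcealed or that the results are biased; the text shows neither. The change is worth making because it is cheap. Confidence is medium, since the enabling conditions cannot be checked from the documents.

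**What to change.** **If allocation is not yet complete:**
- Replace the fixed block of 4 with a computer-generated list of randomly varying blocks (for example 4 and 6), constrained to 25 per arm, with the sizes not disclosed to recruiters.
- Have existing staff outside recruitment hold the list and release each assignment only after enrolment and baseline measurement are recorded.
- Do not show recruiters the running allocation record.
- State in the protocol who generates, holds and releases the list.

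Controlled release and withholding past allocations give the main protection. Varying the blocks cuts certain predictions from about 32% to about 6–9%, but leaves best-guess accuracy near 69%.

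**Cost:** one new list and some time from one existing staff member; no extra subjects, visits or measurements. The downside is that temporary imbalance can reach 3 subjects instead of 2.

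**If allocation is already complete:** a new list cannot help. Report how the sequence was generated, held and released, whether subjects were allocated singly or together, and whether recruiters knew the block size or saw past allocations. Limit the conclusions accordingly, in particular those that rest on the post-study comparison.

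### Baseline significance tests say little about the randomisation, and the between-group comparisons leave out the baseline values that the trial already collects

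*Combined protocol and SAP*

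**What the plan says.** The second bullet of the Statistical Analysis Plan states how comparability before treatment was checked: "randomization of EXP and KTR groups was tested using independent sample t-testing for mean differences or chi-square testing for differences in proportions". It gives no significance level, no list of variables and no action to follow from a significant or non-significant result.

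The next bullet sets out the treatment comparison: "Between-group effects were analyzed in terms of post-study and pre-post differences (Δ/delta) measurements, using independent samples t-testing for normally distributed data", with Mann-Whitney for non-normal data. No baseline covariate is named anywhere, and neither of the two comparisons is designated as the main one.

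Methods item 5 describes allocation "using block of 4 randomization until there were 25 subjects in each group". Methods item 4 lists what is measured before and after. The fitness measures are VO₂max together with "grip strength, sit and reach, and back extension, which was measured using the CSEP protocol"; the laboratory entry reads "Blood work for HbA1c, malondialdehyde (MDA) level, and superoxide dismutation (SOD) activity"; the entry on body size and fat gives "body mass index (BMI) and body fat percentage"; and the patient-reported entry is "Quality of Life measure using the EuroQol EQ-5D questionnaire". A baseline value of every outcome is therefore available.

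**The concern.** If allocation is properly random, any baseline difference is due to chance. A small p-value then only reports that chance has produced a difference, and a large one with 25 per arm does not establish balance. The tests answer neither of the questions they seem to be asked.

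What matters for the treatment effect is how baseline enters the main comparison. Here it enters not at all (post-study values) or by plain subtraction (changes). Given a particular chance imbalance, both estimates are off target in expectation, in opposite directions, unless r is 0 or 1. In a trial of 50 people, two analyses of the same outcome could therefore disagree noticeably, with nothing in the plan to say which is the result. Precision that the collected baseline values could supply is also lost.

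**Working it through.** The documents state no alpha, SD, target difference or sample-size calculation, so there is no figure of the plan's own to reproduce.

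**Inputs from the documents.** 25 per group. Ten before-and-after measures: four fitness, three blood, two body composition, and EQ-5D counted as one score.

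**Assumed, because not stated.** Two-sided alpha 0.05; the ten measures are the variables tested; pairwise correlation among them 0 to 0.7; pre-post correlation r of 0.3 to 0.9; equal SD before and after; complete data.

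**1. Chance of at least one significant baseline difference under sound randomisation.**
- Ten independent tests: 1 − 0.95¹⁰ = 40.1%.
- Simulated with equally correlated normal measures, 25 per arm, 20,000 runs: 37% at correlation 0.2, 29% at 0.5, 22% at 0.7.
- Sensitivity, independent tests: 4 variables 19%, 12 variables 46%, 15 variables 54%. For ten variables, 10% at alpha 0.01 and 65% at alpha 0.10.

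**2. Largest imbalance that a t-test would pass.** t(0.975, 48 df) × √(2/25) = 2.011 × 0.283 = 0.569 SD. At alpha 0.01 it is 0.76 SD; at alpha 0.10 it is 0.47 SD.

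**3. Carry-over of an imbalance d into the two planned mean comparisons.** Expected shift in the post-study difference: r × d. Expected shift in the change difference: (r − 1) × d. The gap between them is d whatever r is, because with complete data the post-study difference minus the change difference is the baseline difference. The last two columns give the type I error conditional on this d (normal approximation).

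| r | Post-study shift (SD) | Change shift (SD) | Type I, post-study | Type I, change |
|---|---|---|---|---|
| 0.3 | +0.171 | −0.398 | 8.1% | 17.0% |
| 0.5 | +0.284 | −0.284 | 13.5% | 13.5% |
| 0.7 | +0.398 | −0.171 | 22.0% | 10.2% |
| 0.9 | +0.512 | −0.057 | 36.5% | 6.7% |

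The table uses d = 0.569. As an example, take the post-study test at r = 0.7. It rejects beyond 1.96 × 0.283 = 0.554. Given d, the difference has mean 0.398 and SD 0.283 × √(1 − 0.49) = 0.202. The upper tail starts at (0.554 − 0.398)/0.202 = 0.77 SD, which gives 22%.

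This d is the extreme that still passes. At d = 0.28 SD, about one standard error of the baseline difference, the shifts at r = 0.7 are +0.196 and −0.084 SD, and the conditional type I error is not above 5% for either comparison (3.8% and 4.9%).

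**4. Effect of adjustment.** In a linear ANCOVA on the outcome's baseline value, the expected shift from d is 0 at any r. The SE relative to each planned comparison is:
- against post-study values, √(1 − r²): 0.87 at r = 0.5, 0.71 at 0.7, 0.60 at 0.8;
- against changes, √(1 − r²)/√(2(1 − r)) = √((1 + r)/2): 0.87, 0.92 and 0.95 at the same r.

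**The case against.** The strongest reply is that the baseline tests do no harm to the treatment estimate. The plan attaches no consequence to them, the main comparisons are unadjusted whatever they show, and deleting them would change no effect estimate. That stands: the carry-over comes from the missing adjustment and would be the same if no baseline test were run. A reader might infer that a non-significant test is the plan's licence not to adjust, or that a significant one would be declared a failure of randomisation. The documents state no such rule.

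It can also be said that chance imbalance is already covered by the standard error. That stands too: over all randomisations the unadjusted tests keep their type I error. The loss is in bias given the imbalance that occurred, and in precision.

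A flat 40% false-alarm rate would be too strong. It needs an alpha, a count of variables and independence, none of which the plan gives. BMI with body fat, or the fitness measures with each other, are plausibly correlated. It would also be too strong to say that an imbalance of 0.57 SD passes whole into the post-study comparison; only r times it does, and the change comparison planned in the same sentence is shifted the other way.

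Finally, the null is true by design only if allocation was not subverted. The protocol describes blocks of 4 and no explicit concealment of upcoming assignments, so some look at baseline has a rationale. But a p-value below 0.05, expected somewhere in roughly a fifth to two fifths of sound trials, is weak evidence of subversion.

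**Conclusion.** The point holds in a limited form. The baseline tests are uninformative about randomisation and can make the baseline table misleading, with a false-alarm rate of about 22–40% under the stated assumptions (higher if demographic variables are tested as well).

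The substantive matter is the absence of baseline adjustment. For an imbalance just short of significance, the two planned mean comparisons are pulled apart by 0.57 SD, split between them according to an r that the documents do not give, and no primary comparison is named. Smaller imbalances shift the estimates proportionately less. Whether such shifts matter clinically cannot be judged, since the documents give no target difference. This is a worthwhile improvement to the plan and does not make the planned comparisons invalid.

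**What to change.** For each outcome, name one main between-group analysis: ANCOVA of the post-study value on group and the baseline value of that same outcome, specified in advance and applied whatever the baseline table shows. For outcomes now sent to Mann-Whitney, specify a transformation or a rank-based ANCOVA, and say how the choice will be made. Pre-post changes can still be reported descriptively. Replace the baseline tests with a descriptive table by group (mean and SD, median and IQR, or counts) without p-values.

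The cost is small. No new data are needed; the model uses one further degree of freedom, and skewed outcomes take somewhat more work.

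### Each outcome is tested twice, on post value and on change, with neither named primary and no baseline covariate; a single ANCOVA per outcome would settle which result counts and usually be more precise

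*Combined protocol and SAP*

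**What the plan says.** The third bullet of the Statistical Analysis Plan reads "Between-group effects were analyzed in terms of post-study and pre-post differences". Each of the two quantities is compared between arms "using independent samples t-testing for normally distributed data" and by "independent samples Mann-Whitney U testing for non-normally distributed data". Nothing in the document says which of the two is primary, and no alpha, multiplicity rule or covariate is given.

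Baseline values are available: Methods item 4, headed "Before and after measurements", covers fitness, blood work, body composition and quality of life. Apart from the subtraction inside the change score, the plan uses baseline only in the second SAP bullet, where "randomization of EXP and KTR groups was tested using independent sample t-testing for mean differences or chi-square testing for differences in proportions". No action follows from that test. Methods item 5 sets the size, "using block of 4 randomization until there were 25 subjects in each group".

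**The concern.** HbA1c, VO₂max, MDA and SOD carry the three objectives (safe, effective, beneficial). Each will have two between-group p-values, with no rule for which one decides. A reader cannot tell whether an effect needs one significant result, both, or a particular one, and the choice could be made after the results are seen.

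Both planned comparisons also use baseline less well than they could. The post-value test ignores it. The change test subtracts it with a slope fixed at 1, whatever the real relation. With 25 per arm, moderate chance differences at baseline are to be expected. Once such a difference has occurred, the two comparisons are pushed in opposite directions. A significance test of baseline differences neither corrects this nor says what to do about it.

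**Working it through.** The plan states no figure to reproduce.

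**Inputs.** From the document: 25 per arm (Methods item 5), and two tests per outcome with no covariate (SAP, third bullet). Assumed, because the document is silent: two-sided 0.05 per test, normal data, SD equal to 1 in both arms before and after, pre-post correlation ρ of 0.5 to 0.8, and a true effect of 0.5 SD for the power figures.

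**1. False positives if either test may count.** Under the null, the correlation between the post and change statistics is (1 − ρ)/√(2(1 − ρ)) = √((1 − ρ)/2). This is 0.50, 0.39 and 0.32 at ρ = 0.5, 0.7 and 0.8. The bivariate normal then gives the chance that at least one is significant; the ceiling for independent tests is 1 − 0.95² = 9.75%. Simulated t-tests at 25 per arm (100,000 trials per ρ) gave 9.1%, 9.4% and 9.5%. Each single test, and ANCOVA, stayed at about 5%. Over ρ from 0 to 0.95 the bivariate-normal figure runs from 8.3% to 9.7%.

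**2. Disagreement.** With a true 0.5 SD effect, exactly one of the two planned tests was significant in 33% (ρ = 0.5), 41% (0.7) and 48% (0.8) of 200,000 simulated trials per ρ.

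**3. Precision and power.** The variance of the group difference, relative to the post-value comparison, is:
- post: 1
- change: 2(1 − ρ)
- ANCOVA: (1 − ρ²)(1 + 1/46), where the second factor is the average cost of estimating the slope with 50 patients

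Power is from the noncentral t with 48 degrees of freedom (47 for ANCOVA). The noncentrality is 0.5/√(variance × 2/25).

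| ρ | Variance: change | Variance: ANCOVA | Power: post | Power: change | Power: ANCOVA |
|---|---|---|---|---|---|
| 0.5 | 1.00 | 0.766 | 41% | 41% | 51% |
| 0.7 | 0.60 | 0.521 | 41% | 61% | 67% |
| 0.8 | 0.40 | 0.368 | 41% | 78% | 81% |

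As equivalent extra patients after the slope cost, ANCOVA against change is worth 1.00/0.766 = 1.31, 0.60/0.521 = 1.15 and 0.40/0.368 = 1.09, that is 31%, 15% and 9%. Against post it is worth 1/0.766 = 1.31, 1/0.521 = 1.92 and 1/0.368 = 2.72, that is 31%, 92% and 172%.

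**4. Effect of a chance imbalance D at baseline.** Given D, with no treatment effect, the expected post difference is ρD and the expected change difference is ρD − D = (ρ − 1)D. The standard error of D is √(2/25) = 0.283 SD. At ρ = 0.7:
- Median imbalance: 0.674 × 0.283 = 0.19 SD. The post comparison shifts by 0.7 × 0.19 = +0.13 SD and the change comparison by −0.3 × 0.19 = −0.06 SD.
- Largest gap that the baseline t-test would not flag: 2.011 × 0.283 = 0.57 SD, at about the 95th percentile. The shifts are 0.7 × 0.57 = +0.40 SD and −0.3 × 0.57 = −0.17 SD.

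**The case against.** The strongest reply is that the 9% arises from having two tests and no rule, not from the lack of ANCOVA. Naming either planned test as primary would also restore 5%. That is correct. ANCOVA earns the precision and removes the conditional shift; designating a single analysis restores the error rate.

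The 9% is also conditional. The SAP does not say that one significant result suffices. If both had to be significant, the rate would be about 0.9%, 0.7% and 0.6% at ρ = 0.5, 0.7 and 0.8. This also stands, but it shows how much the plan leaves open: roughly 0.6% to 9.5% per outcome.

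The precision gain depends on ρ, which the document does not give for any outcome. Against the better of the two planned tests, after the slope cost, it is worth about 8% more patients at ρ = 0.3 (1/0.930) and 2% at 0.2. ANCOVA loses 1% to 2% at ρ of 0 to 0.1. Near 0.9 the change test is almost as good (97% against 98% power). So the gain is real over the middle of the range, and the worst loss is small.

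The figures assume normal data and t-tests, so they do not measure the gain for outcomes that would go to Mann-Whitney. Finally, ANCOVA leaves multiplicity across outcomes untouched: with MDA, SOD, HbA1c and VO₂max at one test each, the chance of some false positive is up to 1 − 0.95⁴ = 18.5% if they are independent.

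**Conclusion.** The concern holds. The plan runs two unadjusted comparisons per outcome, ranks neither, and makes no covariate adjustment. Each test is valid over all randomisations, so this is something the sponsor should change and not a fatal flaw.

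If either result may count, the error rate per outcome is close to double the nominal level, and this varies little with the correlation. For a moderate true effect, contradictory results in a third to a half of trials are the more practical problem, because the plan has no way to resolve them. For correlations of 0.5 to 0.8, ANCOVA beats the better planned test by 9% to 31% in equivalent sample size. These sizes rest on the assumed alpha, correlations, normality and equal SDs. The absence of a decision rule does not.

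**What to change.** - Make one ANCOVA per outcome, with post value as response and group and that outcome's baseline as predictors, the single primary between-group analysis.
- Report the adjusted EXP minus KTR difference with its 95% confidence interval and p-value.
- Fix in advance any transformation for outcomes expected to be skewed. Where none is suitable, as may be so for the EQ-5D score, specify a rank-based ANCOVA.
- Keep the unadjusted t and Mann-Whitney comparisons as sensitivity analyses only.
- Present baseline characteristics descriptively and drop the significance tests.

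The cost is SAP wording and one degree of freedom per outcome, with no new data or patients. The document is written in the past tense and does not settle whether outcome data had been seen. If they had been analysed, the ANCOVA must be labelled post hoc and shown beside the planned tests; it then informs interpretation but cannot undo the original ambiguity. Multiplicity across the outcomes needs a separate rule.
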